2.2.3. Sustained off treatment (36 and 48 weeks after end of treatment) responses

- a. ALT \leq 38 U/L (males), \leq 25 U/L (females) corresponding to approximately 1.25 xULN.
- b. HBV DNA $<$ 1000 IU/mL.
- c. HBV DNA $<$ 1000 IU/mL AND ALT \leq 38 U/L (males), \leq 25 U/L (females) corresponding to approximately 1.25 xULN.
- d. HBV DNA $<$ 20 IU/mL (LLOQ of COBAS Ampliprep/COBAS TaqMan HBV v2.0 test).

2.2.4. Sustained off treatment (36 and 48 weeks after end of treatment) responses in participants with low end of treatment HBsAg levels ($<$ 2000 IU/mL) versus participants with high end of treatment HBsAg levels (\geq 2000 IU/mL)

- a. Cumulative HBsAg loss.
- b. HBeAg loss.
- c. HBsAg seroconversion.
- d. HBeAg seroconversion.
- e. ALT normalization (males \leq 30 U/L, females \leq 20 U/L).
- f. HBV DNA $<$ 1000 IU/mL.
- g. HBV DNA $<$ 20 IU/mL (LLOQ of COBAS Ampliprep/COBAS TaqMan HBV v2.0 test).

2.2.5. Sustained off-treatment (36 and 48 weeks after end of treatment) responses in participants with a substantial drop of HBsAg levels (\geq 1 log from baseline to end of treatment) versus participants who did not have substantial drop of HBsAg levels ($<$ 1 log from baseline to end of treatment)

- a. Cumulative HBsAg loss.
- b. HBeAg loss.
- c. HBsAg seroconversion.
- d. HBeAg seroconversion.
- e. ALT normalization (males \leq 30 U/L, females \leq 20 U/L).
- f. HBV DNA $<$ 1000 IU/mL.
- g. HBV DNA $<$ 20 IU/mL (LLOQ of COBAS Ampliprep/COBAS TaqMan HBV v2.0 test).

2.2.6. Sustained off-treatment (36 and 48 weeks after end-off treatment) responses in participants with end of treatment HBsAg level $<$ 2000 IU/mL and HBV DNA below 1000 IU/mL versus participants with end of treatment HBsAg levels \geq 2000 IU/mL and HBV DNA \geq 1000 IU/mL

- a. Cumulative HBsAg loss.
- b. HBeAg loss.

- c. HBsAg seroconversion.
- d. HBeAg seroconversion.
- e. ALT normalization (males \leq 30 U/L, females \leq 20 U/L).
- f. HBV DNA $<$ 1000 IU/mL.
- g. HBV DNA $<$ 20 IU/mL (LLOQ of COBAS Ampliprep/COBAS TaqMan HBV v2.0 test).

2.2.7. Treatment failure- Cumulative rates of primary nonresponse, partial virologic response and confirmed virologic breakthrough

2.2.8. Rate of discontinuation of treatment due to adverse events.

2.2.9. Rates of adverse events and serious adverse events.

3. Study design

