6.3. Baseline visit (day 0)

The baseline visit (day 0) will coincide with randomization and the start of therapy. The baseline visit will consist of:

1. Limited clinical evaluation.
2. Review of adverse events and concomitant medications.
3. Drug dispensing; instructions on their use, including education on self-injection with peginterferon alfa-2a (if appropriate).
4. Questionnaires (symptoms, quality of life, health behaviors, and fatigue).
5. Depression assessment.
6. Blood tests including CBC with differential, hepatic and renal panel, albumin, total protein, alkaline phosphatase, and PT/INR.
7. Urinalysis, urine creatinine, and urine phosphate.
8. Pregnancy test for females of childbearing potential.
9. A blood sample for storing serum and plasma for future research.
10. Blood samples for qualitative HBeAg, anti-HBe, quantitative HBsAg, quantitative HBeAg, and HBV DNA testing.
11. Blood sample (with consent) for DNA extraction and genetic testing will be drawn if not obtained as part of the Cohort Study. This may be collected at a future visit if not obtained at baseline.

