8.1.1. Analysis of primary endpoint

The primary endpoint is loss of HBsAg at week 240. The cumulative proportion of HBsAg loss at the designated time-point will be estimated using the product-limit (Kaplan-Meier) estimate. HBsAg loss between two treatment groups will be compared using a Wald-type two-sided two-sample proportion test (chi-square test).

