8.1.2. Analysis of secondary endpoints

Analysis of secondary endpoint listed in 2.2.1a: *To compare the cumulative proportion HBsAg loss over time during and after treatment*

Cumulative proportion of HBsAg loss over time will be calculated using the product limit (Kaplan-Meier) method. HBsAg loss between two treatment groups will be compared using a two-sided two-sample stratified log-rank test. We will also describe the treatment effects in terms of hazard rates of HBsAg-loss and corresponding 95% confidence intervals. To take into account the stratification at randomization, we will use stratified Cox proportional hazard models. Comparison of hazard rates of HBsAg loss across two treatment groups adjusting for other baseline demographic, virological and clinical characteristics such as age, race, genotype, HBeAg status, initial HBV DNA level, and baseline histology will be performed using Cox proportional hazard regression. The results will be presented as incidence rate ratios of HBsAg loss and 95% confidence intervals.

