8.2. Missing data

Primary analyses will be performed using all enrolled participants (intention-to-treat analysis). For the primary analysis, the proportion of patients with HBsAg loss at the end of follow-up (week 240) will be estimated using the product limit (Kaplan-Meier) method which includes drop outs for as long as they are followed. Since our sample size estimation accounts for participants lost to follow up for various reasons, and due to randomization, the rate of missing is expected to be similar in the two treatment groups, we will also conduct the analysis of primary endpoint on the available cases. For this analysis, we will describe the treatment effects in terms of relative risks and 95% confidence intervals. In order to take into account the stratification at the randomization, we will use Mantel-Haenszel chi-square test. Comparison of rates of HBsAg loss across two treatment groups adjusting for other baseline demographic, virological and clinical characteristics such as age, race, genotype, HBeAg status, initial HBV DNA level, and baseline histology will be performed using multivariable log-linear (Poisson) regression, with HBsAg loss (Yes/No) as the outcome. The results will be presented as relative risks of HBsAg loss and their 95% confidence intervals.

In general, the procedure of missing outcome data will be handled as follows in statistical analyses. First, we will explore the pattern of missing data by comparing characteristics of participants with available data to those with missing data. For data missing completely at random (does not depend on observed outcome; MCAR) standard analytical techniques described earlier would produce unbiased results when the analysis is performed on the complete data. For the time-to-event data analyses, the analytical methods such as Kaplan-Meier method, log-rank test, and Cox proportional hazard model automatically accounts for MCAR drop-outs. However, in other cases, we will assume that the dropout depends on observed outcome and/or covariates (missing at random, MAR). For such scenarios, likelihood-based methods such as mixed models, generalized linear mixed models and logistic regression will provide unbiased inference. For GEE, we will draw inference using inverse-probability-weighting approach, with models fitted using the reciprocal of the estimated probability of missing as weights. The probability of missing will be estimated using logistic regression.

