8.3. Sample size and power

The sample size for this study was determined based on the primary endpoint of HBsAg-loss at 48 weeks after treatment has been stopped. There are no data available on HBsAg loss for long-term treatment with tenofovir DF or tenofovir DF and peginterferon combination therapy. We anticipate that after 192 weeks of treatment and 48 weeks of follow-up post-treatment 5% of the participants in the tenofovir DF alone group will achieve HBsAg loss compared to 15% participants in the tenofovir DF and peginterferon combination therapy group. The clinical trial would require 141 participants per arm (282 participants in total) to detect this expected difference with 80% power at 5% level of significance using a two-sided test of equality between two proportions (chi-square test). However, for this long-term treatment trial, it is expected that approximately 25% of the participants will be lost to follow-up and hence the study will recruit a total of 376 participants (randomized 1:1 to two treatment arms, 188 per arm) to account for the missing participants.

9. Data and safety monitoring board

Data and safety will be monitored by the NIDDK in conjunction with an NIDDK-appointed Data and Safety Monitoring Board (DSMB). This board serves in a consultative capacity to inform the NIDDK decisions regarding conduct of the study. The description of DSMB activities is included in the DSMB Charter.

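### The adjusted models for HBsAg loss use open covariate lists that do not name the day-0 quantitative HBsAg level; it should be pre-specified

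*Combined protocol and SAP*

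**What the plan says.** **Collected.** Section 6.3 (baseline visit, item 10) schedules day-0 blood for a set of tests that includes "quantitative HBsAg, quantitative HBeAg, and HBV DNA testing", with no condition attached. Section 8.1 gives HBsAg level, beside HBV DNA, as an example of a continuous baseline variable to summarise. It also plans tests comparing baseline viral characteristics between the arms.

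**Adjusted models.** The Cox model for HBsAg loss in 8.1.2 adjusts for "characteristics such as age, race, genotype, HBeAg status, initial HBV DNA level, and baseline histology will be performed using Cox proportional hazard regression". Section 8.2 gives the same examples for an available-case analysis of the primary endpoint by "multivariable log-linear (Poisson) regression, with HBsAg loss (Yes/No) as the outcome". Section 8.1.2.1 repeats the list twice: in a Poisson sentence that also names HBsAg loss as the outcome, and in a Cox sentence for other time-to-event endpoints. HBsAg level is in none of the four.

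**Analyses without such a list.** The primary comparison in 8.1.1 has no covariates: "HBsAg loss between two treatment groups will be compared using a Wald-type two-sided two-sample proportion test (chi-square test"). The stratified log-rank and stratified Cox analyses (8.1.2) and the Mantel-Haenszel test (8.2) account for the randomisation factors only.

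**The concern.** The endpoint is disappearance of HBsAg, and the amount of HBsAg at the start is the nearest thing to it that the trial measures before treatment. HBV DNA, a less direct measure, appears in every list; HBsAg level appears in none.

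Two things follow for the adjusted estimates. First, 8.1 will show any between-arm difference in baseline viral measures, but no rule says what is then done. An open list lets this covariate be added or left out after results are known. Second, if baseline HBsAg predicts loss, a model without it may forgo precision and is exposed to chance imbalance in it. Few events are expected, so either effect could be noticeable. What is at stake is the quality of the secondary and supportive estimates, not the primary test.

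**Working it through.** **1. The plan's own figure.** Inputs from the sample size section: "5% of the participants in the tenofovir DF alone group will achieve HBsAg loss compared to 15% participants" on combination therapy, "with 80% power at 5% level of significance using a two-sided test of equality between two proportions (chi-square test"). With pooled variance under the null and mean rate 0.10:

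n per arm = [1.960·√(2·0.10·0.90) + 0.842·√(0.05·0.95 + 0.15·0.85)]² / 0.10² = [0.8315 + 0.3521]² / 0.01 = 140.1, rounded up to 141.

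This matches the text: "The clinical trial would require 141 participants per arm (282 participants in total"). Inflating for 25% loss gives 282/0.75 = 376, also as stated. Power at 141 per arm is 80.3%. None of this involves a covariate, so nothing below alters it.

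**2. Events.** 141·0.05 + 141·0.15 = 7 + 21, or about 28 among completers.

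**3. Power with and without one baseline covariate.** The documents give no prognostic strength for baseline HBsAg, so a range is assumed. About 4,000 trials were simulated per setting, with 141 per arm, full follow-up, overall loss held at 5% and 15%, and a standard-normal covariate acting proportionally on the hazard. Cox and Poisson models (the latter with robust variance, which the plan does not specify) were fitted with arm alone, then with arm and covariate.

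| Assumed hazard ratio per SD | Cox, without → with | Poisson, without → with |
|---|---|---|
| 1.00 | 80.6% → 80.5% | 80.0% → 80.2% |
| 0.78 | 80.0% → 79.8% | 79.5% → 79.6% |
| 0.61 | 80.9% → 81.5% | 80.4% → 80.9% |
| 0.47 | 81.5% → 83.7% | 81.2% → 83.3% |
| 0.37 | 80.8% → 84.8% | 80.3% → 83.9% |
| 0.22 | 80.9% → 91.4% | 80.2% → 87.9% |

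The Monte Carlo standard error of each figure is √(0.8·0.2/4000) = 0.6 points. The changes in the first three rows are no larger than that. The gain is about 2 points at 0.47, about 4 at 0.37, and 8 to 10 at 0.22.

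The baseline model here holds arm only. The planned models may already contain HBeAg status, genotype and HBV DNA, so these gains are upper-end values.

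**4. Chance imbalance.** In SD units, the standard error of the between-arm difference in the baseline mean is √(2/141) = 0.119. One trial in 20 therefore has a difference beyond 1.96·0.119 = 0.233 SD. The resulting shift in an unadjusted hazard comparison is roughly:

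- hazard ratio 0.61 per SD (log −0.5): exp(0.5·0.233) = 1.12
- hazard ratio 0.37 per SD (log −1.0): exp(1.0·0.233) = 1.26
- hazard ratio 0.22 per SD (log −1.5): exp(1.5·0.233) = 1.42

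For scale, the planned rates imply a hazard ratio between arms of ln(0.85)/ln(0.95) = 3.17. Again, stratified randomisation and covariates that share the signal would reduce these shifts.

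**The case against.** The strongest reply is that nothing has been excluded. Each list gives examples of baseline demographic, virological and clinical characteristics, and HBsAg level is a virological characteristic. A reader might infer that the plan deliberately leaves it out; the text does not say so. This part of the objection stands. What remains is that an open list does not pre-specify the covariate.

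Three further readings go too far:

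- **That every adjusted analysis of HBsAg loss is affected.** The stratified log-rank, stratified Cox and Mantel-Haenszel analyses carry no such list.
- **That the trial wastes power.** The powered test is unadjusted. The plan sets no power target for the adjusted models, and the gain there is nil unless baseline HBsAg is fairly strongly prognostic.
- **That the plan itself treats baseline HBsAg as the key predictor.** Section 2.2.4 concerns "participants with low end of treatment HBsAg levels" against those with high levels, 2.2.6 also uses end-of-treatment level, and 2.2.5 uses the decline on treatment. These are post-randomisation markers. Section 2.2.5 does need the baseline value, but only to compute the decline. Nor is the level strictly the baseline value of the endpoint: the endpoint is binary, and inclusion criterion 3 requires every participant to be HBsAg positive at entry.

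A fair caution is that about 28 events support few parameters. Arm plus the six named characteristics, at one parameter each, already gives 28/7 = 4 events per parameter. Higher parameter counts depend on category numbers that the plan does not state. Arm, three randomisation factors and log10 HBsAg would give 28/5 = 5.6. Whether age, race and histology stay in the model is a matter of preference, and this point does not turn on it.

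**Conclusion.** The point holds as a minor matter of pre-specification. The adjusted models for HBsAg loss in 8.1.2 and 8.2, and the Poisson sentence in 8.1.2.1 that names that outcome, do not commit to using a baseline measure that the trial collects and that lies closest to the endpoint.

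The benefit of naming it falls on secondary and supportive estimates: no later choice about this covariate, protection against chance imbalance, and a power gain from nil to about 10 points at 141 per arm. The upper end needs a hazard ratio per SD of about 0.22. The figures rest on the assumed range of prognostic strength, a normally distributed covariate, proportional hazards and complete follow-up. The primary two-proportion test, its 80.3% power and the 376 recruited are unchanged.

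**What to change.** In 8.1.2 (adjusted Cox) and 8.2 (adjusted Poisson), name log10 day-0 quantitative HBsAg as a covariate for HBsAg loss, together with the randomisation factors: HBeAg status, genotype A versus others, and cirrhosis. Replace the open list with a closed one fixed before the data are examined by arm. Where the Poisson sentence in 8.1.2.1 is meant to apply to HBsAg loss, have it refer to the same list. Leave 8.1.1 and the sample size section as they are.

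The cost is SAP wording only, since the measurement is already scheduled at day 0.

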8.1.2.1. Analyses of other secondary endpoints

Secondary endpoints for this clinical trial are listed in sections 2.2.1 – 2.2.9. These endpoints could be grouped into several different classes. The first group of endpoints we will deal with are binary endpoints characterized by the occurrence of some event by a fixed time point. These events include HBeAg loss, HBeAg seroconversion, HBsAg seroconversion, normalization of ALT, ALT \leq 1.25 X ULN, HBV DNA $<$ 1000 IU/mL, HBV DNA $<$ 20 IU/mL, absence of detectable antiviral drug-resistance HBV mutations, treatment discontinuation, and treatment failure. Analysis will be conducted separately for these events at the designated time points listed in sections 2.2.1-2.2.9

Proportion of such an event (e.g. proportion of HBeAg loss) between two treatment groups will be summarized using 95% confidence intervals and will be presented graphically by using bar charts. The rate of occurrence of an event between two treatment groups will be compared using a two-sided two-sample proportion test (chi-square test or Fisher's exact test as appropriate). We will also describe the treatment effects using relative risk of the event and corresponding 95% confidence interval. In order to take into account the stratification at randomization, we will use Mantel-Haenszel chi-square test. Comparison of rates of an event across two treatment groups adjusting for other baseline demographic, virological and clinical characteristics such as

age, race, genotype, HBeAg status, initial HBV DNA level, and baseline histology will be performed using multivariable log-linear (Poisson) regression, with HBsAg loss (Yes/No) as the outcome. The results will be presented as relative risks of the event and their 95% confidence intervals.

Time to such events may also be of interest (e.g. cumulative HBeAg loss, time to treatment failure). For time-to event analysis, Kaplan-Meier curves will be used to plot the cumulative proportion of events over time by treatment groups. The cumulative proportions will then be compared using two-sided stratified log-rank test. The treatment effect will be described using hazard rate of the event and corresponding 95% confidence interval. In order to take into account the stratification at randomization, we will use stratified Cox proportional hazard models. Comparison of hazard rates of an event across two treatment groups adjusting for other baseline demographic, virological and clinical characteristics such as age, race, genotype, HBeAg status, initial HBV DNA level, and baseline histology will be performed using Cox proportional hazard regression. The results will be presented using hazard rates and 95% confidence intervals.

The second group of endpoints is continuous variables such as changes in ALT, HBV DNA levels from baseline at designated treatment or follow-up time points. Descriptive statistics, including measures of central tendency (e.g. means, medians) and estimates of spread (e.g., standard deviations, quartiles) will be used to characterize such changes. Student's t-test or a non-parametric alternative, the Wilcoxon rank-sum test, will be used to determine differences in the distribution of these changes between the two treatment arms. Multiple regression analyses will be conducted to assess the association between baseline characteristics and these changes. Spearman or Pearson correlation coefficients will be used to measure the strength and direction of the association between such changes and other participant characteristics. Scatter plots will be used to display the association between continuous variables.

The third group of variables consists of variables that are measured over time (longitudinal data) such as quantitative HBV DNA levels. For graphical representation over time, we will use spaghetti plots of original data (e.g. HBV DNA levels) and summarize the pattern of data across subgroups (e.g. genotype, treatment groups) over time by using means (for continuous outcome) or proportions (for binary outcomes). To determine the significance of change in continuous outcome over time across treatment group adjusting for other baseline and longitudinal participant characteristics, we will use mixed models if the data are normally distributed or generalized estimating equations (GEE) if deviation from normality is evidenced. These approaches simultaneously model the regression of the response variable on the independent variables and account for the correlated nature of the responses. Analyses using conventional regression methods could provide erroneous variance estimates and loss of statistical efficiency because of the conventional assumption that each response is statistically independent. As a result, invalid inferences could be made if the conventional approach were applied to these longitudinal data. A similar approach of analysis will be adopted (generalized linear mixed model or GEE) for longitudinal binary or count outcomes over time.

The results will be summarized using rate of change/odds ratio/relative risk over time and the corresponding confidence intervals. Interaction between treatment and participant characteristics will be investigated to assess the differential effect of treatments across subgroups of participants (e.g. genotypes).

Secondary endpoints that are defined within a specific subgroup will be analyzed only for participants in that subgroup. For example, sustained off treatment (36 and 48 weeks after end of treatment) responses will be assessed only among those whose treatment was discontinued at week 192.

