Thus, the advantages of nucleos(t)ide analogue therapy are the ease of administration, the lack of significant side effects and the consistent suppression of HBV DNA that can be achieved, particularly with the newer agents such as tenofovir DF and entecavir. While emergence of drug resistance can limit the efficacy of oral agents, a low rate of antiviral resistance (1% or less even with prolonged therapy for 4 to 5 years), is seen with entecavir and tenofovir DF, reflective of their greater potency and higher genetic barrier to resistance. As a consequence 80-90% of patients treated long-term with these agents achieve rates of marked suppression of HBV DNA levels and normal ALT levels. The advantage of peginterferon therapy is that it is administered for a limited period (6 to 12 months) and results in loss of HBsAg in a significant proportion of patients. Previous studies have shown that a one-year course of combination therapy of peginterferon and nucleos(t)ide analogue does not yield a higher response rate than a one-year course of either agent alone (21). However, these studies have been limited by the use of a nucleos(t)ide analogue with high risk of resistance (e.g. lamivudine) and a relatively short course of treatment. Thus, an obvious question is whether the combination of a limited course of peginterferon (6 or 12 months) with long-term therapy with a potent nucleos(t)ide analogue (tenofovir DF or entecavir for at least 4 years) will provide a higher rate of loss of HBsAg and ability to stop therapy without relapse. This clinical trial compares the efficacy of peginterferon plus a potent nucleotide analogue, tenofovir DF, for 24 weeks followed by monotherapy with tenofovir DF for a further 3.5 years to the efficacy of that same potent nucleotide analogue, tenofovir DF, given for a full 4 years. The primary measure of outcome will be HBsAg loss in serum 240 weeks after starting antiviral therapy.

2. Study objectives

To define the role of limited duration peginterferon alfa-2a in the presence of tenofovir for treating people with chronic hepatitis B by:

- Evaluating “off treatment” sustained responses following combination therapy consisting of peginterferon alfa-2a plus tenofovir DF versus tenofovir DF monotherapy.
- Comparing the on-treatment efficacy of initial treatment with combination therapy consisting of peginterferon alfa-2a plus tenofovir DF versus tenofovir DF monotherapy.

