2.2. Secondary endpoints

2.2.1. At week 192 :

- a. Cumulative HBsAg loss.
- b. HBeAg loss.
- c. HBsAg seroconversion.
- d. HBeAg seroconversion.
- e. ALT normalization (males \leq 30 U/L, females \leq 20 U/L).
- f. ALT \leq 38 U/L (males), \leq 25 U/L (females) corresponding to approximately 1.25 xULN.
- g. HBV DNA $<$ 1000 IU/mL.
- h. HBV DNA $<$ 20 IU/mL (Lower limit of quantification [LLOQ] of COBAS Ampliprep/COBAS TaqMan HBV v2.0 test).
- i. Absence of detectable antiviral drug-resistance HBV mutations.
- j. Sustained HBV DNA $<$ 1000 IU/mL

2.2.2. Sustained end of follow-up responses at week 240

- a. Cumulative HBsAg loss.
- b. HBeAg loss.
- c. HBsAg seroconversion.
- d. HBeAg seroconversion.
- e. ALT normalization (males \leq 30 U/L, females \leq 20 U/L).
- f. HBV DNA $<$ 1000 IU/mL.
- g. HBV DNA $<$ 20 IU/mL (LLOQ of COBAS Ampliprep/COBAS TaqMan HBV v2.0 test).

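### The adjusted model for ten other binary endpoints names HBsAg loss as its outcome, and its Poisson regression of yes/no data has no stated variance estimator

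*Combined protocol and SAP*

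**What the plan says.** Section 8.1.2.1 defines a first group of binary endpoints and names ten: HBeAg loss, HBeAg seroconversion, HBsAg seroconversion, ALT normalization, ALT up to 1.25 times ULN, HBV DNA below 1000 IU/mL, HBV DNA below 20 IU/mL, no detectable resistance mutations, treatment discontinuation and treatment failure. It adds: "Analysis will be conducted separately for these events at the designated time points listed in sections 2.2.1-2.2.9".

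For each event it plans a chi-square or Fisher test, a relative risk with a 95% interval, and a stratified test: "In order to take into account the stratification at randomization, we will use Mantel-Haenszel chi-square test". It then gives the covariate-adjusted comparison as a multivariable Poisson regression "with HBsAg loss (Yes/No) as the outcome. The results will be presented as relative risks of the event and their 95% confidence intervals".

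Section 8.2 uses nearly the same sentence for the available-case analysis of the primary endpoint: "log-linear (Poisson) regression, with HBsAg loss (Yes/No) as the outcome. The results will be presented as relative risks of HBsAg loss".

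Neither section says how the variance of the Poisson estimates is to be obtained. Section 8.1.2.1 does warn about wrong variance estimates, but only for correlated longitudinal responses. The inverse-probability weighting in section 8.2 concerns GEE only.

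**The concern.** There are two faults in one sentence.

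**Outcome.** The adjusted model is introduced as a comparison of an event's rates and reported as a relative risk of that event, but its dependent variable is fixed as HBsAg loss. That variable is not among the ten events. Nothing later in section 8.1.2.1 or in section 8.2 corrects this.

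**Variance.** A Poisson model takes the variance of the response to equal its mean, p. A yes/no response has variance p(1-p). Model-based standard errors are therefore too large, and increasingly so as the event becomes common. Several of the listed endpoints may be common. The Background expects that "80-90% of patients treated long-term with these agents achieve rates of marked suppression of HBV DNA levels and normal ALT levels", and it describes resistance as rare: "a low rate of antiviral resistance (1% or less even with prolonged therapy for 4 to 5 years". One of the ten endpoints is "Absence of detectable antiviral drug-resistance HBV mutations", which would then occur in about 99%.

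For such endpoints the report could show a significant planned test beside an adjusted interval that comfortably includes 1. A reader could conclude that adjustment had removed the effect, when only a software default had widened the interval.

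**Working it through.** **Outcome: the passages side by side**

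| | Section 8.1.2.1 | Section 8.2 |
|---|---|---|
| Endpoint under analysis | each of ten listed events | HBsAg loss |
| Outcome named in the model | HBsAg loss | HBsAg loss |
| Relative risk reported | of the event | of HBsAg loss |
| Consistent? | No | Yes |

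The parallel Cox paragraph in section 8.1.2.1 is worded generically, for an event. That indicates what was meant here.

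**Variance: inputs.** From the sample size section: 5% vs 15%, 141 evaluable per arm, 188 recruited per arm, 25% loss. From the Background: 80-90%, and resistance of 1% or less. All other rates are assumptions, because the plan gives none by arm for the secondary endpoints.

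**The plan's own figure first.** With p1 = 0.05, p2 = 0.15 and mean 0.10:

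n = [1.96 × sqrt(2 × 0.10 × 0.90) + 0.8416 × sqrt(0.05 × 0.95 + 0.15 × 0.85)]² / 0.10² = 140.1, so 141 per arm.

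282 / 0.75 = 376. Both figures reproduce, and nothing below changes them.

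**Formulas.** For two arms of n with a and b events:

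- model-based Poisson variance of log RR = 1/a + 1/b
- binomial (robust) variance of log RR = 1/a + 1/b - 2/n

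At a common rate p the ratio of standard errors is 1/sqrt(1-p), whatever n is.

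**Standard error ratios, model-based over binomial**

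| Rates | Calculation | Ratio |
|---|---|---|
| 5% vs 15% | sqrt(26.67/24.67) | 1.04 |
| 30% both | 1/sqrt(0.70) | 1.20 |
| 50% vs 60% | sqrt(3.667/1.667) | 1.48 |
| 80% both | 1/sqrt(0.20) | 2.24 |
| 80% vs 90% | sqrt(2.361/0.361) | 2.56 |
| 90% both | 1/sqrt(0.10) | 3.16 |
| 99% both | 1/sqrt(0.01) | 10 |

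**Worked table, 150/188 vs 169/188.** RR = 169/150 = 1.127; log RR = 0.1193.

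- Model-based SE = sqrt(1/150 + 1/169) = 0.1122; 95% CI 0.90 to 1.40; p = 0.29.
- Robust SE = sqrt(1/150 + 1/169 - 2/188) = 0.0441; 95% CI 1.03 to 1.23; p = 0.007.
- Chi-square p = 0.006; Fisher p = 0.009.

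A fitted Poisson model with default and sandwich errors gives the same two standard errors.

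**With 25% lost, 113/141 vs 127/141.** RR = 1.124; chi-square p = 0.019; CI 0.87 to 1.45 model-based (SE 0.129) and 1.02 to 1.24 robust (SE 0.050).

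**Power, 400,000 simulated trials per scenario, 188 per arm**

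| Rates | Chi-square | Robust interval excludes 1 | Model-based interval excludes 1 |
|---|---|---|---|
| 50% vs 60% | 50.9% | 48.6% | 16.3% |
| 80% vs 88% | 56.6% | 56.6% | 0.3% |
| 80% vs 90% | 78.3% | 78.3% | 1.1% |

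At 80% vs 90%, when chi-square is significant the model-based interval still includes 1 in 98.7% of trials.

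**With covariates.** In 1,000 simulated trials of 376 participants with four assumed covariates, at 80% vs 88%, the empirical SD of the adjusted log RR was 0.046, the mean robust SE 0.046 and the model-based SE 0.114.

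**The case against.** **The outcome is an obvious slip.** The surrounding text makes the intention plain, and no analyst would refit HBsAg loss ten times. The list of events is also not closed, so HBsAg loss at other time points (2.2.2a, and 2.2.4a to 2.2.6a) might fall under this section, where that outcome would be right. Both points are fair, but the sentence still cannot serve the ten events it names. A prespecified model should not depend on the analyst overriding its stated outcome.

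**The variance harm is conditional, conservative and confined.** Nothing in the plan says that model-based errors will be used. If they were, type I error would fall: a nominal 5% test would have actual size of about 3.4% at a 15% rate and 0.6% at 50%. Section 8.1.2.1 also plans an unadjusted relative risk with its interval, so an anomaly would be visible. All of this stands and limits the weight of the point.

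**The striking figures need high rates.** The Background gives HBeAg loss of 12-35% at one year, and section 5.3.3 gives peginterferon discontinuation of 6-9%. There 1/sqrt(1-p) is only 1.03 to 1.24. The 80-90% figure describes on-treatment response, whereas the plan's ALT cut-offs are specific to it and many of its endpoints are off treatment. This also stands: the inflation is large only for whichever endpoints prove common.

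**Robust variance has limits.** It can be slightly too small when events are few, which matters for HBsAg seroconversion and for the subgroup whose treatment stopped at week 192.

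**Conclusion.** Both parts hold. The outcome named in section 8.1.2.1 is wrong for the ten events listed there, and this rests on the text alone. The missing variance estimator is an omission that matters only if default standard errors are used. The standard errors of the adjusted log relative risks would then be inflated by 4% at 5% vs 15%, by about half at 50% vs 60%, and 2.2- to 3.2-fold across 80-90%. Apart from 5% vs 15%, these rates are assumptions, and the contrasts between arms are illustrative.

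The effect is limited to the covariate-adjusted relative risks and intervals for binary outcomes. The primary test, the sample size, the chi-square, Fisher and Mantel-Haenszel tests, and the time-to-event, continuous and longitudinal analyses are untouched. The plan should be corrected, but the trial's main conclusion is not at risk.

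**What to change.** 1. In section 8.1.2.1, replace HBsAg loss as the outcome of the adjusted model with *the event under analysis (Yes/No)*.
2. In sections 8.1.2.1 and 8.2, add *with robust (sandwich) variance* to the Poisson regression. In 8.2 this is mainly for consistency: at 5% vs 15% the adjusted SE is 0.380 robust and 0.396 model-based.
3. For absence of resistance mutations, report the planned Fisher comparison without an adjusted model if resistance is as rare as the Background suggests. One percent of 376 is about 4 non-events, and of 282 about 3. The denominator is itself uncertain, since Appendix 3 ties the testing to patients with detectable HBV DNA.

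A log-binomial model would also have the right variance, but it may not converge. Unconstrained fits failed in 44-64% of simulated trials at 80-90%, depending on starting values, so robust Poisson is preferable here. Where events are few, the robust interval should be read with the small-sample caution noted above.

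The cost is three short wording changes and a standard software option, with no new data and no change in sample size.
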